2.2 Current treatments and their limitations

Current therapies have focused on agents which block the host immune response. Over 30 trials of immune blockers have failed to improve survival in sepsis.(25) These failures have led to a reevaluation of the pathophysiology of sepsis and new therapies consisting of agents that boost host immunity.(2) New trials with GM-CSF and IFN- γ , drugs which enhance immune function are underway in sepsis.(26)(27)

2.3 Study product: glycosylated recombinant human CYT107 “CYT107”

CYT107 has critical roles in T cell development and may restore at multiple levels the immunologic situation specifically by restoring adequate T cells count.(8)(9)(10). CYT107 that will be employed in the present clinical trial is the current glycosylated form of recombinant human CYT107 and is produced in engineered CHO mammalian cells. This form shows less immunogenicity in primates and is expected to be less/non-immunogenic in humans. Furthermore, as discussed below, its pharmacokinetic and dynamic profile may allow for a greater interval between administrations. CYT107 has been assessed in humans and results of

toxicity studies performed in cynomolgus macaques after one cycle of treatment are summarized in section 4.3 of the investigator brochure.

2.3.1 Quantitative and functional effects of CYT107

The quantitative and functional effects of CYT107 are comprehensively reviewed in the Investigator's Brochure and briefly summarized in the table below, demonstrating how administration of CYT107 may help to meet several of the unmet medical needs.

Table 1 : Main immunological properties of IL7

Quantitative impact
 
 • Development and expansion of CD4+ and CD8+ $\alpha\beta$ T cells: naive, and memory subpopulations • Development and expansion of $\gamma\delta$ T cells and natural killer thymic (NK T) cells 
Functional impact
 
 • Decrease frequency of “exhausted” PD-1 CD4+ and CD8+ T cells • Decrease apoptosis (increase of anti-apoptotic Bcl-2 protein, decrease of pro-apoptotic Bim protein) • Decrease frequency of regulatory T cells (Tregs) • Increase cytotoxicity of CD8+ T cells • Co stimulation of T cells: 
 ➢ Increase reactivity of T cells against weak immunogens / subdominant epitopes ➢ Increase differentiation and survival of central memory T cell

Pre-clinical studies

The available preclinical and clinical results of CYT107 underscore its therapeutic potential to restore adequate CD4+ T cells counts and improve immune protection.

IL-7 plays a key role in thymopoiesis

IL-7 has critical and non-redundant roles in T cells development, hematopoiesis, and post-developmental immune functions as a prototypic homeostatic cytokine.(8-10) IL-7 also supports T cells survival by up-regulating members of the anti-apoptotic Bcl-2 family, and by down-regulation of the pro-apoptotic activity In contrast to IL-2, CYT107 therapy in humans induces robust and functional CD4+ T cells expansion without selective expansion of Treg cells.(10) In addition, CYT107 therapy increases T cells receptor (TCR) repertoire diversity and increases circulating TCR rearrangement excision circles (TRECs) numbers, which have been used as an indirect measure of thymic output because they reflect TCR gene recombination events and are enriched within the RTE fraction (13). CYT107 signals through the CYT107 receptor, which is composed of the CYT107R α (CD127) and the common gamma (γ) chains.

2.3.1.1 Inverse correlation between CD4+ T cells lymphopenia and circulating IL-7

An inverse correlation between CD4+ T cells lymphopenia and circulating IL-7 has been consistently documented after any infectious or iatrogenic lymphopenia, implicating endogenous IL-7 in the regulation of T cell homeostasis(28). In HIV-infected patients, elevated CYT107 levels gradually decline as CD4+ T cells recovery occurs following effective anti-retroviral therapy. Importantly, several studies suggest that IL-7 drives CD4+ T cells restoration subsequent to the suppression of HIV replication. (12) IL-7 circulating levels are particularly high in patients benefiting from an exceptionally successful and fast immune restoration.²⁸

2.3.1.2 Experimental effects of CYT107 in HIV/SIV infection

a) Expansion of CD4+ T cells

A sustained increase in CD4+ T cells and a parallel expansion of CD8+ T cells has been consistently demonstrated in SIV-infected monkeys treated by CYT107,(29) before being confirmed in humans which were performed using CYT 99 007 (1st generation non-glycosylated CYT107/ E.Coli r-hCYT107) and CYT107 (glycosylated r-hCYT107 CYT107).(30)(12).

b) Enhancement of anti-HIV/SIV T cells responses

The pleiotropic quantitative or functional effects of CYT107 converge to improve T cells response against HIV:

- CYT107, because of its co-stimulatory effect, may increase the magnitude and breadth of anti HIV CD4+ and CD8+ T cells responses;
- CYT107 increases cytotoxicity of specific anti-HIV CD8+ T cells, as shown *ex vivo* with T cells derived from HIV-infected donors;
- CYT107 may foster the differentiation, of protective memory CD4+ and CD8+ T cells, which is typically blocked and/or outnumbered by the accumulation of exhausted CD127^{low} effector memory T cells. Thus r-hCYT107 may alter the balance between CD127^{low} exhausted and CD127^{high} protective T cells in favor of the latter subpopulation.

The drug is well tolerated and the most frequent adverse events observed are local erythema at injection site. (12-14, 31)

Activity

[figure not shown]
Recent trials in HIV-infected patients have demonstrated a sustained dose-dependent increase in naïve and memory CD4⁺ and CD8⁺ T cells after administration of r-hCYT107 either with CYT 99 007 or CYT107.(12,30,31) In a prospective randomized placebo-controlled study, a single subcutaneous (SC) dose of r-hCYT107 was well tolerated with biologic activity demonstrable at 3 µg/kg and a maximum tolerated dose (i.e. without SAE or dose limiting toxicity) of 30 µg/kg. Single-dose of recombinant r-hCYT107 increased the numbers of circulating CD4⁺ and CD8⁺ T cells, predominantly of central memory phenotype. Levy et al.¹ published recently the preliminary results of the CYTHERIS study. These results were based on 13 patients who received a total of 8 subcutaneous injections of 2 different doses of r-hCYT107 (CYT 99 007); 3

or 10 µg/kg, 3 times per week (w) over a 16-day period. R-hCYT107 was well tolerated and induced a sustained increase of naive and central memory CD4+ and CD8+ T cells. (12)

We have now confirmed and extended our initial results with the completion of the INSPIRE study conducted in USA, Canada, France, Italy, utilizing the current glycosylated version of r-hCYT107 (CYT107) in HIV patients whose disease was well controlled by HAART but who remained immune non-responders with CD4+ T cells counts below 400/µL.

[figure not shown]
Results from INSPIRE patients confirmed the ability of CYT107 to produce a high quality immune recovery as shown in figure 2. The increases of CD4+ T cells counts induced by the three dosages of CYT107 administrations (10, 20 and 30 µg/kg/week) were significant when compared to the levels observed in the placebo arm (12).

Figure 2 Dose-dependent effect of CYT107 (CYT107) on CD4+T cells

At 20 µg/kg, CYT107 (CYT107) preferentially expanded Naive (N) and Central memory (CM) CD4+ as shown in figure 3.

[figure not shown]
Figure 3 Expansion of Naive (N) and Central Memory (CM) T cells after CYT107, 20 µg/kg

X axis is the ALC/µL. Y axis represents Days (D) or Weeks (W).

[figure not shown]
This expansion was associated with a significant decrease of the “PD-1⁺” exhausted CD4⁺ and CD8⁺ T cells as shown in figure 4:

Figure 4 Decrease of exhausted (PD1⁺) CD4⁺ and CD8⁺ T cells after CYT107

In addition, a clear support of thymopoietic production, was demonstrated by the increase in TREC ratio, recent thymic emigrants and naïve T cells (see figure 5)

[figure not shown]
Figure 5 increase in TREC ratio, recent thymic emigrants and naïve T cells

Various results from the INSPIRE study demonstrated the quality of CYT107-induced T cells reconstitution in these “Immune Non Responding” patients:

- CYT107 administration was clinically and biologically well tolerated
- 20 µg/kg/week was the dose with the best efficacy/safety ratio
- A single cycle (3 subcutaneous injections) induced a rapid and sustained increase of CD4+ and CD8+ T cells, with most patients (5/8) treated with 20 µg/kg of CYT107 reaching CD4+ T cells counts > 500 cells/µL at W12
- CYT107 induced a brisk expansion of T cells subsets – increasing RTE, naïve, central memory and effector T cells
- The increase in CD4 and CD8 T cells is long lived and persists for a number of months (Figure 6)

Figure 6 Long-term increase of CD4+ after CYT107 administration.

These results demonstrate that the effect of CYT107 to increase the ALC persists for a number of weeks after cessation of therapy. Given the high rate of recurrent infections that persist for up to one year in septic patients following hospital discharge (Journal of Intensive Care 29:87-95 2014), this CYT107 induced increase in ALC may be highly beneficial.

Going forward, RevImmune is currently considering various new studies with CYT107 (CYT107) in oncology as well as in sepsis.

[figure not shown]
2.4 Rational for an CYT107 clinical trial in sepsis

CYT107 is an essential, non-redundant, pluripotent cytokine produced mainly by bone marrow and thymic stromal cells that is required for T-cell survival.(8,9) In addition to its anti-apoptotic properties, CYT107 induces potent proliferation of naïve and memory T-cells potentially supporting replenishment of the peripheral T-cell pool which is severely depleted during sepsis.(10) CYT107 also reverses T cell “exhaustion” and increases expression of cell adhesion molecules which improve the ability of T-cells to traffic to sites of infection.’12) Unlike other closely related common γ -chain cytokines such as IL-2, CYT107 does not induce a hyper-inflammatory “cytokine storm” response and has been remarkably well-tolerated.(8)

Because of CYT107’s ability to boost and restore CD4 and CD8 T cell function, key components of the adaptive immune system, it was hypothesized that CYT107 would be efficacious against invading pathogens. Subsequent studies have proven this hypothesis to be correct. (16, 18) CYT107 has shown efficacy in improving morbidity and mortality against diverse pathogens. (16,18) CYT107 restored cytokine secretion, improved T cell trafficking to the site of infection, and decreased tissue viral load in a mouse model of lymphocytic choriomeningitis.(11) CYT107 reversed lymphopenia and T cell exhaustion and improved T cell repertoire diversity in rhesus macaques with simian immunodeficiency virus.(29) Several independent laboratories have shown that CYT107 improves survival in a clinically relevant bacterial peritonitis model.(16,32) Most recently, CYT107 has been shown to improve survival in a clinically-relevant, two-hit model of fungal sepsis.(18)

Importantly, there is increasing evidence that CYT107 will be highly effective in clinical infectious disease. CYT107 reversed T cell exhaustion and restored T cell functionality in HIV patients who were non-responders to HAART.12,(32) CYT107 increased T cell receptor diversity in HIV patients with lymphopenia and in patients who had lymphopenia following radiation or chemotherapy for treatment of acute myelogenous leukemia.(12,13) In a subset of patients with hepatitis C who were non-responders to conventional therapy, CYT107 lead to complete clearing of virus from the blood (33). CYT107 also lead to clearing of the JC virus in a lymphopenic patient with progressive multifocal leukoencephalopathy (PML).(17) Subsequently, 10 additional patients with PML have been treated with CYT107 on a compassionate basis and have had beneficial responses including clearing of virus (personal communication [name] – former CEO of Cytheris).

Figure 7 Beneficial Effects of CYT107 in Sepsis

CYT107 has numerous and diverse effects to improve immune function in sepsis including: i) decreases in sepsis-induced apoptosis, ii) increased production of T cells with diverse T cell receptors (TCRs), iii) decreasing PD-1 expression with reversal of T cell exhaustion, iv) increased IFN- γ production, v) increased integrin expression leading to improved T cell trafficking to infected sites.^{6,7,16,18} Thus, CYT107 is ideally suited to treat patients with sepsis because it directly reverses key immunologic defects in the disorder.

2.4.1 Rationale of the Clinical Study: the need to reconstitute adequate lymphocyte counts in sepsis In conclusion, CYT107 reverses a fundamental defect in sepsis, i.e., the massive loss of lymphocytes. CYT107 has been highly effective in improving survival in clinically relevant animal models of sepsis.^(16,18,34) It offers great promise in the treatment of septic patients.

Therapeutic immune reconstitution should be:

- *Strong and stable*: meaning to allow patients to recover peripheral CD4+ T cells counts to above the 500 cells / μ L for the duration of the study period,
- *Deep*: meaning not only involving peripheral CD4+ T cells recovery but also inducing a T cells repopulation of lymph nodes and gut mucosa,
- *Diverse*: involving both CD4+ and CD8+ T cells, naïve and memory,
- *Functional*: limiting over-activation (CD38+HLADR+), exhaustion (PD1+), and production of Treg cells while preserving functionality (CD28+).

- *Broad*: supporting thymic activity and facilitating the recovery of the peripheral TCR repertoire.

2.4.2 Study Population

Patients selected in this trial will have severe sepsis with documented lymphocytopenia consisting of an absolute lymphocyte count (ALC) of less than 900 cells per microliter. (ALC <900/ μ L). Also see Inclusion criteria.

2.4.3 Investigational Medicinal Product – glycosylated recombinant human IL-7 (CYT107)

2.4.3.1 Route

CYT107 will be administered intra-muscularly or subcutaneously based on hemostasis results and whether patients are receiving anticoagulant and antifibrinolytic treatments. If the patient receives anticoagulant and/or antifibrinolytic therapy, intramuscular route is contraindicated. In that case, CYT107 will be administered subcutaneously.

By subcutaneous route, according to the monkey studies results, CYT107 bioavailability is satisfactory (> 75%) with an extended kinetic profile which may favor prolonged CYT107 activity. But the sub-cutaneous route is known to favor recombinant proteins immunogenicity, accordingly following the recent example of beta interferon, these new CYT107 studies will be mainly performed by intra-muscular administration. Depending on haemostasis results (INR greater than 2.5 or a platelet count less than 35,000), CYT107 will be administrated subcutaneously. This explains why the present study also includes the assessment of PK profile in these patients (35)(36)(37).

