--------------------------	---

Study Design	
This is a phase II, double-blinded, randomized, placebo-controlled study aimed at comparing, two dosing frequencies in lymphopenic patients with sepsis.
 
The study will be performed in the US. A twin study will be performed in France using the same study design so that a common statistical analysis could be performed at the end of the two studies.
 
Patients will be randomized to three arms; CYT107 High Frequency Arm, CYT107 Low Frequency Arm, and Control (standard of care), with a ratio of 1:1:1
 
BLINDING: Patients and care-providers will be blinded as well as outcome assessors.

Sample Size	
A total of 30 evaluable septic patients from US and French sites will be randomized 1:1:1 to receive study drug treatment over 4 weeks:
 
• High frequency: intramuscular (IM) administration of CYT107 at 10µg/kg x2/week x 4 wks (total of 8 doses of CYT107)• Low frequency: IM administration of CYT107 at 10µg/kg x2/ the first week followed by CYT107 and Placebo weekly for 3 wks(total of 5 doses of CYT107 + 3 doses of Placebo)• Control: Will receive 8 administrations of Placebo (twice a week for 4 wks)

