3.2 Secondary Objectives

3.2.1 To characterize CYT107 pharmacokinetics (PK) in this patient population

Another secondary objective of the study is to examine the pharmacokinetics (PK) and pharmacodynamics (PD) of CYT107 in patients with sepsis. Septic patients frequently have changes in circulating blood volume, impaired vasculature integrity with leakage of proteins into the interstitial space, and organ dysfunction. Although the investigators expect that CYT107's main PK parameters in septic patients will not be substantially affected by these alterations, it is important to define CYT107 AUC, C_{max} and half-life in this patient population. This information can be used to guide the proper dosing of CYT107 in a larger trial.

Up to now, CYT107 was administered by sub-cutaneous route to patients, but this route of administration is susceptible to increase the immunogenicity of the drug and patient's edema which is frequent in sepsis patients might alter the bioavailability. In this study the CYT107 product will be preferentially given by intra muscular administration. As exemplified for Interferon by Munafo et al(35), FSH by Steinkampf (36) et al., Alefacept by Sweetser (37) et al. and Onercept by Trincharde-Lugan (38) et al., the IM route is known to deliver pharmacokinetic profiles very similar to the S.C. route. Nevertheless the PK profile of CYT107 administered by I.M. will be determined during the study. Nevertheless, septic patients are susceptible to development of coagulopathy, which increases the risk of complications associated with

intramuscular drug administration. Thus, CYT107 will be administered via the subcutaneous route in coagulopathic (INR>2.5, platelet count less than 35,000/ul) patients.

3.2.2 To characterize CYT107 Pharmacodynamics - To determine if CYT107 can restore depressed functional activity of immune effector cells in patients with sepsis.

We will look at the ability of CYT107 to improve common markers of immune function that have been shown to correlate with outcome in patients with sepsis. Note that these tests are not standardized clinically available tests but rather tests that may be useful in the future to help guide administration of immunotherapeutic agents. These tests will be performed in the 3 investigators laboratories by their laboratory technicians.

- Effects to increase monocyte HLA-DR expression
- Effects to increase whole blood LPS-stimulated TNF- α

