4.2 Study Treatment

Up to thirty patients may be enrolled at 4 sites in the US, i.e., Vanderbilt, Ohio State, University of Florida, and Washington University School of Medicine, however, it is anticipated that the initial enrollment of 30 subjects will occur at Vanderbilt, Washington University and Limoges in France. (Note: the French sites may also enroll up to 30 patients such that a total of 30 evaluable patients will be available from the two countries). In the event that patient accrual is delayed in one country, all patients will be recruited from either the US or France alone. A computerized protocol will implement permuted block randomization in blocks of size three. This scheme ensures balance across the treatment groups for every third randomization. A maximum of 20 septic patients will be treated with CYT107 at a dose of 10µg/kg. There will be two dosing regimens as illustrated in Figure 8 (below). CYT107 will be administered intramuscularly at the dose of 10µg/kg (IBW), once or twice a week for a four week cycle. Ten septic patients will have CYT107 administered twice a week for 4 weeks. Ten septic patients will have two doses of CYT107 administered during the first week followed by one dose of CYT107 in conjunction with 1 dose of placebo for 3 additional weeks. Ten septic patients will receive placebo twice a week for four weeks along with routine standard of care per the clinical providers.

At approx. 48-120 hrs **after admission** for sepsis, those septic patients who meet the Inclusion/Exclusion criteria (see previous section) and provided written informed consent, will be entered into the study. The first dose of CYT107 (as indicated below) is at approx. 48-120 hrs after sepsis onset. The initial dose of study drug will be administered only in the ICU by the PI or research nurse. If patients have an INR greater than 2.5 or a platelet count less than 35,000, CYT107 will be administered by the subcutaneous route rather than by intra-muscular injection.

A staggered approach to CYT107 treatment will be used in which treatment will not be initiated in a newly enrolled patient until 24 hours after the previously enrolled patient has received the second dose of CYT107 without evidence of serious adverse event (SAE) occurrence.

In patients with coagulopathy (INR greater than 2.5 or a platelet count less than 35,000), CYT107 will be administrated subcutaneously.

Figure 8 Schematic study design of CYT107 Protocol

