8.1.6 CYT107 Preparation

Syringes containing the CYT107 dose (placebo dose same volume of NaCl 0.9%) will be prepared by the hospital pharmacy and delivered to the clinic in a blinded fashion. The product

should be defrosted at least 1 hour before administration. Defrosted product (and possibly put in syringe) should be kept refrigerated at +4°C/+8°C until use and for no more than 12 hours.

CYT107 ampoule will only be used if the solution is clear (following visual inspection), the vial is undamaged and the use by (expiration) date (if marked on the vial) has not been passed.

Based on patient's ideal body weight on day of study entry, the appropriate number of vials of CYT107 drug product will be prepared and administered. CYT107 will be kept refrigerated until time of immediate administration to the patient. To minimize the chance for contamination, sterile or septic technique should be carefully observed during CYT107 solution preparation (filling of the syringe) and administration.

A vial is restricted for use by a single patient. Take no more than 0.5 mL into the syringe. The dose to be injected will be divided as necessary into multiple intramuscular injections so that each injection will not exceed 0.5 ml in volume. (Dosing guidelines for ideal body weight make the requirement for multiple injections highly unlikely).

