8.4 Study Drug Administration

Each dose of CYT107 or Placebo will be administered in the hospital by a trained research nurse or PI. CYT107 or Placebo will be administered by intramuscular route at the dose of 10 µg/kg based on the patient's ideal body weight unless the patient meets criteria for subcutaneous injection (see Sect 4.2 Study Treatment).

The volume to be administered will be identical in all groups: 0.005mL/kg: ex: 0.375mL for patients of 75kg. The control group will receive the same volume of saline, dosing to IBW.

The detailed procedures to be followed by Pharmacy and hospital are provided in the Pharmacy Manual including a table of volumes to be administered per patient total body weight.

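### Route of injection: Section 2.4.3.1 contraindicates intramuscular dosing for patients on anticoagulant or antifibrinolytic therapy, but Sections 8.4 and 4.2 direct it unless a laboratory threshold is crossed

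*Protocol*

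**What the plan says.** Protocol Section 2.4.3.1 (Route) says that the route is chosen "based on hemostasis results and whether patients are receiving anticoagulant and antifibrinolytic treatments". It then says: "If the patient receives anticoagulant and/or antifibrinolytic therapy, intramuscular route is contraindicated". The sentence after that sends such patients to SC dosing. Later the same section gives INR above 2.5 or platelets below 35,000 as a further ground for SC.

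Section 8.4 (Study Drug Administration) directs IM dosing for both CYT107 and placebo "unless the patient meets criteria for subcutaneous injection (see Sect 4.2 Study Treatment". Section 4.2, to which it points, gives the criteria twice: "If patients have an INR greater than 2.5 or a platelet count less than 35,000, CYT107 will be administered by the subcutaneous route" and, further down, "In patients with coagulopathy (INR greater than 2.5 or a platelet count less than 35,000), CYT107 will be administrated subcutaneously". Neither sentence mentions concomitant therapy.

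Section 3.2.1 also gives the laboratory thresholds alone: "CYT107 will be administered via the subcutaneous route in coagulopathic (INR>2.5, platelet count less than 35,000/ul) patients". Section 8.1.6 (CYT107 Preparation) considers only IM dosing; a large dose is to be "divided as necessary into multiple intramuscular injections so that each injection will not exceed 0.5 ml in volume". The synopsis gives IM with no exception in both places where it describes treatment: under Sample Size ("High frequency: intramuscular (IM) administration of CYT107 at" the stated dose) and under Study Treatment.

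**The concern.** Section 2.4.3.1 stands in the Background and Rationale chapter, but it is worded as an instruction and uses the language of contraindication. Staff preparing or giving a dose would work from Section 8.4, which sends them to Section 4.2. Neither place tells them that anticoagulant or antifibrinolytic therapy matters. Following those two sections exactly can give a patient an injection that the protocol itself says must not be given by that route.

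The stake is patient safety. Section 3.2.1 recognises that disordered coagulation in sepsis raises the risk of complications from IM injection. The schedule has up to eight injections per patient. Because Section 8.4 covers placebo as well, control patients are exposed to the same conflict.

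Section 2.4.3.1 also does not say which therapy counts: no agent, no dose, and no distinction between prophylactic and therapeutic use. Even a site that found the rule could not apply it consistently.

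**Working it through.** No figure in the plan bears on this point, so the check is a comparison of texts.

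**Step 1. What each section says about route.**

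| Protocol section | Default route | Therapy sends patient to SC? | INR >2.5 or platelets <35,000 sends patient to SC? |
|---|---|---|---|
| 2.4.3.1 | mainly IM | yes | yes |
| 3.2.1 | preferably IM | not mentioned | yes |
| 4.2 | IM | not mentioned | yes (stated twice) |
| 8.4 | IM | only through 4.2, so no | only through 4.2, so yes |
| 8.1.6 | IM only | not mentioned | not mentioned |
| Synopsis (Sample Size; Study Treatment) | IM only | not mentioned | not mentioned |

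Three sections state SC criteria (2.4.3.1, 3.2.1, 4.2), and the therapy criterion is in 1 of the 3. Counting every section that mentions the route, with the synopsis as one, it is in 1 of 6: one with therapy and laboratory criteria, two with laboratory criteria only, one that defers to 4.2, and two with IM and no exception (1 + 2 + 1 + 2 = 6).

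**Step 2. Trace each type of patient through the rules.** The complement of INR >2.5 or platelets <35,000 is INR ≤2.5 and platelets ≥35,000.

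| Patient | Under 2.4.3.1 | Under 8.4 with 4.2 | Agree? |
|---|---|---|---|
| Past either threshold, on therapy or not | SC | SC | yes |
| INR ≤2.5 and platelets ≥35,000, not on therapy | IM | IM | yes |
| INR ≤2.5 and platelets ≥35,000, on therapy | SC (IM contraindicated) | IM | **no** |

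The conflict is confined to the third row.

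**Step 3. Can such a patient be in the trial?** The exclusion criteria (Section 5.2 and synopsis) and the prohibited medications (Section 8.8.2) name neither anticoagulants nor antifibrinolytics. These patients can be enrolled and dosed.

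**Step 4. Do the laboratory thresholds stand in for the therapy criterion?** Nothing says so. Section 2.4.3.1 names haemostasis results and therapy as two separate bases and gives each its own sentence. PTT is measured (Sections 6.1 and 6.3.2), but no route rule uses it.

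**The case against.** The best case against the point is that Section 4.2 gives a sufficient condition for SC dosing. It does not say that SC is used only when a threshold is crossed, and no sentence says that anticoagulated patients receive IM. Someone who reads the whole protocol can satisfy 2.4.3.1, 3.2.1 and 4.2 together by giving SC whenever any trigger is met. On this view the defect is an incomplete cross-reference. That is right for those three sections taken alone. It fails once Section 8.4 is added, because 8.4 makes IM the rule and takes its exception from 4.2 and nowhere else.

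A second argument concerns severity. The number affected is unknown, the Pharmacy Manual might carry the contraindication, doses are given in hospital by trained staff, each injection is limited to 0.5 mL, and the DSMB reviews treatment-emergent events as they occur. All of this is true, and the real harm could be small. But none of these safeguards sets the route, and a correct manual would leave the protocol contradicting itself.

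A third argument is that 1 of 6 overstates the imbalance. Section 8.1.6 is about dividing volumes, the synopsis omits the laboratory exception as well, and 8.4 only defers to 4.2. That is fair: 1 of 3 is the more telling count, and neither count measures how many patients are affected.

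**Conclusion.** The protocol is wrong as written and must be corrected. For patients on anticoagulant or antifibrinolytic therapy with INR ≤2.5 and platelets ≥35,000, it both contraindicates IM injection and directs it. For all other patients the two rules agree.

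The size of the subgroup cannot be derived: the documents do not give the share of patients on such therapy, and the answer depends on how the undefined therapy is read, above all on whether prophylactic dosing counts. Whether sites would in practice give IM depends also on the Pharmacy Manual, which is not among the documents. The conclusion rests only on the protocol text and assumes nothing about either. No effect on the primary endpoint or its analysis is claimed.

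**What to change.** Put a single list of SC criteria in Section 4.2. Until the sponsor's clinicians decide otherwise, it should read: INR above 2.5, or platelets below 35,000, or current anticoagulant and/or antifibrinolytic therapy. State beside it which agents and what intensity count, and whether prophylactic dosing does. Word the list for study drug in all arms, since Section 8.4 applies the same route rule to placebo.

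The change to 4.2 removes the conflict, because 8.4 already refers there. For consistency, 2.4.3.1, 3.2.1, 8.4 and both synopsis statements should refer to that list, and 8.1.6 should speak of injections by the route set in 4.2. If only the laboratory thresholds are intended, delete the blanket contraindication from 2.4.3.1 instead.

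The cost is one wording amendment touching six sections, one clinical decision on which therapy counts, and a check that the Pharmacy Manual matches. The downside of adding the criterion is more SC dosing. Section 2.4.3.1 links that route to greater immunogenicity, and both it and 3.2.1 prefer IM. How much more depends on the definition, so the definition has to be adopted together with the criterion.
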